# 17.3.2. Acute toxicity study

The first 150 or so patients accrued into the study will be assessed by a healthcare professional for acute skin toxicity up to settling of reaction to RTOG grade 1 and at least 4 weeks post radiotherapy. The patients will also be asked to complete the Radiotherapy Breast Symptoms Diary Cards for self-assessment of acute toxicity. This would enable a rate of RTOG grade≥3 acute skin reactions of 10.9% to be excluded,

based on the data from the 50 Gy in 25 fractions control schedule of the FAST trial. From the FAST trial 5-fraction test schedules, the rate of acute skin reactions is expected to be around 2.3% in the test groups of FAST-Forward. Using the Simon single stage design (using exact p-values) with power 89.2% and one-sided alpha of 7.9%, 50 patients per group will be required (total 150). In each test group, if 3 or more patients develop grade ≥3 acute skin reactions, the IDMC may advise the Trial Steering Committee to consider a change in the test schedule.

#### 17.3.3. QL and photographic sub-studies

For the sub-studies (photographic assessments and quality of life), 732 patients per group (2196 in total) would provide 80% power to detect an 8% difference in the prevalence of late adverse effects at 5 years between the test groups (assuming a 5-year rate of 35%). The calculations allow for up to 10% loss to follow-up / unevaluable.

#### 17.4 Interim analyses and Data Monitoring

The Independent Data Monitoring Committee (IDMC) will review the data on early skin reactions (up to 3 months following treatment) after the first evaluable 150 patients. This is based on data from the FAST Trial that has found a proportion of RTOG grade ≥3 acute skin reactions in the test groups (30 Gy and 28.5 Gy) of 2.3% and 10.9% in the control group (50 Gy). For each test group in the FAST-Forward Trial we would like to rule out a proportion of RTOG grade ≥3 acute skin reactions of 10.9% ( $p_0$ =89.1%). We expect this rate to be around 2.3% ( $p_1$ =97.7%) in the test groups (27 Gy and 26 Gy). Using the Simon single stage design (using exact p-values) with power 89.2% and one-sided alpha of 7.9%, 50 patients per group will be required (total 150). In each test group, if 3 or more patients develop grade ≥3 acute skin reactions, the IDMC may advise the Trial Steering Committee (TSC) to consider a change in the test schedule.

Interim analyses of local tumour control, normal tissue responses, radiotherapy side effects and the other endpoints will be conducted at yearly intervals and presented to the IDMC for confidential review. In the light of the interim analyses, the IDMC will advise the TSC if, in their view, the trial has indicated 'proof beyond reasonable doubt' that one of the schedules is clearly indicated or contraindicated in terms of local tumour control and/or normal tissue responses. In reviewing the evidence, the IDMC will also consider any available data from other randomised trials involving similar comparisons. The TSC may then consider modification or termination of the study. Unless such a

situation arises, the Trial Management Group (TMG), the collaborators and the central administrative staff (except the statistician who prepares the analyses) will remain unaware of the interim results. The IDMC may recommend continuation beyond the planned number of patients in the main trial, the Quality of Life study or in the number of patients having photographic assessments, if it is felt that further information is required to address reliably the hypothesis in question.

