The UK FAST Trial (N = 915) tested two dose levels of a 5-fraction regimen delivering 1 fraction per week against a control schedule of 50 Gy in 25 fractions, defining radiotherapy adverse effects as the primary endpoint [10]. The two test dose levels delivered 5 fractions of 5.7 Gy or 6.0 Gy (total dose 28.5 Gy or 30 Gy), estimated to be iso-effective with the control regimen assuming  $\alpha/\beta$  values of 3.0 Gy or 4.0 Gy, respectively. 915 patients were recruited from October 2004 - March 2007. Mean age was 62.7 years. Only 17 patients (5.2%) developed moist desquamation (12 after 50 Gy, 3 after 30 Gy, 2 after 28.5 Gy) out of 327 with RTOG skin toxicity data available. At a median follow up of 28.3 months (IQR 24.1-33.6), 729 patients had 2-year photographic assessments available, with mild and marked change in breast appearance in 19.3% and 1.7% after 50 Gy, 26.2% and 9.3% after 30 Gy, and 20.3% and 3.7% after 28.5 Gy. Risk ratios for mild and marked change for 30 Gy vs. 50 Gy were 1.48 (95%Cl 1.06 -2.05) and 6.06 (2.14 -17.20), p<0.001 for trend, favouring 50 Gy; and for 28.5 Gy vs. 50 Gy were 1.07 (0.75 -1.54) and 2.25 (0.70 -7.18), p=0.26 for trend, favouring 50 Gy. Any clinically-assessed moderate/marked adverse effects in the

breast were increased for 30 Gy compared with 50 Gy (hazard ratio, HR 2.19, 95%Cl 1.46 - 3.29, p<0.001), but similar for 28.5 Gy (HR 1.33, 95%Cl 0.86 -2.08, p=0.19). At a median follow-up of 37.3 months 2 local tumour relapses had been recorded.

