A gain in local tumour control due to shortening treatment time to 1 week is possible. Evidence based on retrospective studies for an influence of treatment time on local tumour control is conflicting with recent systematic reviews drawing different conclusions [11, 12]. Even without a gain in tumour control, accelerated radiotherapy is likely to be more convenient for patients, and may ease scheduling with other treatment modalities. A pilot study (N = 30) tested 30 Gy in 5 fractions of 6.0 Gy in 15 days to the whole breast in terms of acute adverse effects and late effects at 2 years [13]. In this series, 23/30 (77%) patients scored no change in post-operative breast appearance at 2 years, 7/30 (23%) scored mild change and none scored marked change. The acute skin reactions were mild, with no reaction more severe than grade 2 erythema, scored in 9/30 (27%) patients. If the results of the proposed randomised trial support a 5fraction schedule delivered in 1 week, these will transform international breast radiotherapy practices. In conclusion, it is fair to say that after decades of resistance to evaluating larger radiotherapy fraction sizes in breast cancer, expert opinion is responding to an accumulating body of evidence supporting the safety and effectiveness of this approach.

Against this background, a phase III randomised trial is described with the primary aim of testing local tumour control in women with early breast cancer following a 5-fraction schedule of adjuvant radiotherapy delivered in 1 week. Stratification by treatment centre and by local relapse risk will ensure balanced trial groups (high risk defined as patient age <50 and/or grade 3 tumour; low risk defined as age ≥50 and grade 1 or 2 tumour) [14].

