# APPENDIX 1: Acute skin reactions scoring scale (modified RTOG)

Grade	Description
Grade 0	No visible change
Grade 1	Faint/dull erythema
Grade 2	Tender/bright erythema +/- dry desquamation
Grade 3	Patchy moist desquamation, moderate oedema
Grade 4	Confluent moist desquamation, pitting oedema

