#### **Acute skin reactions**

Data on acute skin reactions in humans suggest that acute skin reactions will be milder in the test groups, since acute reactions are much less sensitive to fraction size than to total dose (which is reduced from 40.05 Gy to <30 Gy in the test groups). A 1 week schedule is too short to stimulate repopulation in the epidermis and radiosensitisation due to re-assortment. This expectation is consistent with the results of a pilot study in 30 patients receiving 30 Gy to whole breast in 5 fractions of 6.0 Gy over 15 days, in which there were 3 cases of grade 1 and 1 case of grade 2 moist desquamation (no cases of grade 3 or 4) [2].

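### The acute-skin rule is computed correctly, but no review is tied to the third event, at which a test group's result is settled

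*Protocol*

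**What the plan says.** Sections 17.3.2 and 17.4 describe a single-stage exact design for each test group. The aim is to "rule out a proportion of RTOG grade ≥3 acute skin reactions of 10.9"%, and of the test groups the protocol says "We expect this rate to be around 2.3"%. Both rates are attributed to the earlier FAST trial. With 50 patients per group the stated power is 89.2% and the one-sided alpha 7.9%.

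The trigger is a fixed count: "In each test group, if 3 or more patients develop grade ≥3 acute skin reactions, the IDMC may advise the Trial Steering Committee (TSC"). Such advice would concern a possible change to that group's schedule. On timing, Section 17.4 says the IDMC "will review the data on early skin reactions (up to 3 months following treatment) after the first evaluable 150 patients".

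Other parts of the protocol bear on this:

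- Section 8.2.1: skin reactions in the first 150 patients are graded weekly during treatment and for 4 weeks afterwards, and longer if they have not settled.
- Section 17.4: yearly interim analyses include radiotherapy side effects.
- Section 19.3: the IDMC meets regularly, at least once a year.
- Section 16.2: serious adverse events are reported within 24 hours.
- Appendix 1: grade 3 is "Patchy moist desquamation, moderate oedema"; grade 4 is confluent moist desquamation with pitting oedema.

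**The concern.** The rule depends only on whether a group reaches three events. Once it has, later patients cannot reverse the result. The protocol nevertheless places the review that uses the rule at a fixed point, after all 150 patients are evaluable, and names no step to be taken when the third event is recorded. A test schedule with a rate near the one to be excluded could meet its trigger about halfway through its 50 patients, and the committee would have no stated prompt to look until the later review. Recruitment is not paused in the meantime, and after the first 150 patients the weekly skin grading is no longer done.

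Two wording problems sit beside this. The calibration rates appear to be moist-desquamation rates, while grade 3 and grade 4 also list oedema, and the text does not say whether oedema alone qualifies. The pilot study's acute reactions are also described in two ways that do not agree with each other or with the trial's scale.

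**Working it through.** **Inputs.** n = 50 per test group; trigger at 3 or more events; rate to exclude 10.9%; expected rate 2.3% (Sections 17.3.2 and 17.4).

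**1. The plan's own figures.** A schedule passes with at most 2 events in 50. With X binomial(50, p):

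- Alpha = P(X ≤ 2 | 0.109) = 0.0031 + 0.0191 + 0.0572 = 0.0794. Stated: 7.9%.
- Power = P(X ≤ 2 | 0.023) = 0.3124 + 0.3677 + 0.2121 = 0.8922. Stated: 89.2%.

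Both reproduce. Allowing 3 events would give alpha 0.191 and power 0.972, so a trigger of 3 or more is the one that matches.

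**2. When the result is settled.** The third event falls at patient k with probability C(k−1, 2) p³ (1−p)^(k−3). Summing over k = 3 to 50 gives the chance of meeting the trigger, and weighting by k gives its timing among groups that meet it.

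| True rate | P(trigger met) | Mean patient number of third event | Patients of the 50 still to come |
|---|---|---|---|
| 2.3% | 10.8% | 36.0 | 14.0 |
| 10.9% | 92.1% | 24.5 | 25.5 |
| 20% (illustrative) | 99.9% | 14.9 | 35.1 |

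At 10.9% the median is patient 23. These counts ignore the delay between treatment and a visible reaction, so they are upper limits on the patients of the 50 that earlier notice could affect.

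**3. Effect of acting at the third event.** The event that three or more of 50 react is the same whether it is noticed at the third reaction or after patient 50. Alpha stays at 7.94% and power at 89.2%.

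**4. Recruitment around the review (assumption: steady accrual).** Section 6.2 gives 4000 patients, and Appendix 3 anticipates 3.5 to 4 years. That is 4000/48 = 83 to 4000/42 = 95 per month. The first 150 would take 150/95 = 1.6 to 150/83 = 1.8 months, and a further 3 months would add about 250 to 286 patients, two-thirds of them (167 to 190) in the test groups. Early accrual is likely to be slower, so these are rough figures.

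**5. Source of the two rates.** Section 2 says "Only 17 patients (5.2%) developed moist desquamation": 12 after 50 Gy, and 3 + 2 = 5 in the test groups, of 327. Of the control denominators tried (105 to 115), only 110 gives both printed rates: 12/110 = 10.9% and 5/217 = 2.3%. The group denominators are not printed, so this is an inference.

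**6. The pilot's acute reactions.** Section 2 says the 30 patients had "no reaction more severe than grade 2 erythema", in 9/30, printed as 27% although 9/30 is 30%. Appendix 2 says of the same study that "there were 3 cases of grade 1 and 1 case of grade 2 moist desquamation (no cases of grade 3 or 4"). Under Appendix 1, moist desquamation first appears at grade 3. The three places cannot all be on one scale.

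**The case against.** The strongest reply is that the rule is sound and other safeguards exist. Its arithmetic is correct. The trigger is advisory, so three events would stop nothing by themselves, either now or with earlier notice. The protocol does not say that the IDMC looks only once: there are yearly analyses that cover side effects, meetings at least annually, 24-hour reporting of serious events and provision for urgent safety measures. IDMC procedures are left to a charter that is not shown. With fast accrual, many of the 50 patients would be treated before a third reaction was known.

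Most of this stands, and it limits the point. It does not close the gap, because none of these routes is linked to the third event. A yearly look can fall later than the 150-patient review, and a grade 3 skin reaction need not meet the definition of a serious event. Fast accrual cuts both ways: it reduces the patients saved among the first 50, but adds patients between the third event and the review.

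Two stronger readings are tempting and are not supported. A reader might infer that the 2.3% and 10.9% do not fit the graded endpoint. But moist desquamation is the skin descriptor of grades 3 and 4, so those counts do map to grade 3 or more; only the status of oedema alone is open, and the protocol gives no oedema rate. A reader might also set the pilot's 4/30 = 13.3% moist desquamation against the 10.9% limit. The pilot used another schedule (30 Gy over 15 days), did not set either design rate, and is not shown to have been graded on the Appendix 1 scale. Its conflicting descriptions need correcting, but they do not undermine the rule.

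**Conclusion.** The point holds as a matter of timing, not of calculation. The design figures are correct and should stay. What is missing is any review or notice tied to the moment the trigger is met. If a test group's true rate were 10.9%, the trigger would be met with probability 92%, on average at about patient 25 of 50 and with a median of 23. About half the group would then come after the result was settled, less those already treated before the third reaction became visible. This assumes independent patients with a constant rate and immediate detection. The numbers beyond 150 depend on an assumed steady accrual and are only indicative.

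This is a cheap improvement to safety monitoring rather than the correction of an error. The oedema wording and the pilot descriptions are minor points.

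**What to change.** In Section 17.4, and in the matching text of Section 17.3.2, keep the trigger at 3 of 50 and keep it advisory. Add that the trial statistician notifies the IDMC in confidence when the third grade 3 or higher skin reaction is recorded in a test group, and that the planned review after 150 evaluable patients still takes place. This fits the existing confidentiality arrangement, under which the statistician who prepares the analyses is the exception among staff kept unaware of interim results. It leaves the committee's discretion intact.

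The cost is prompt forwarding and checking of weekly forms that are already collected. No extra assessments are needed, and alpha and power do not change.

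As minor edits:

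- State whether oedema alone counts as grade 3 or more for this rule, and name moist desquamation as the source of the two design rates if that is confirmed. Do not narrow the event to moist desquamation, which would drop oedema from safety counting.
- Reconcile the pilot's acute reactions between Section 2, Appendix 2 and the Appendix 1 scale, including the 9/30 percentage.

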#### 18. ASSOCIATED STUDIES

At the time of randomisation all patients will be asked to consent to gift a whole blood sample which may be taken at any routine follow up visit, and a formalinfixed paraffin-embedded (FFPE) diagnostic tumour tissue sample.

Sites will be notified by ICR-CTSU to when the sample collection will commence and no samples should be collected prior to this notification.

#### 18.1 Molecular Correlates of Normal Tissue Injury

It is thought that part of the inter-patient variation in the incidence and severity of late normal tissue responses reflects inter-patient differences in tissue responsiveness to radiotherapy. Common DNA sequence variations (single nucleotide polymorphisms) account for differences in protein expression between individuals that may explain an important component of the variation between individuals. Genome-wide approaches offer scope to identify patterns of single nucleotide polymorphisms, DNA copy number and methylation status that may distinguish patients at lower and higher than average annual risk of late adverse effects.

Up to 20 ml of whole blood will be collected by venesection into blood tubes and sent to the Institute of Cancer Research, Sutton, Surrey, where it will be stored for future research, in accordance with the Human Tissue Act 2004. The research may be carried out at other centres, including those outside the UK. An aliquot of this blood may also be requested for comparison of genomic DNA with tumour DNA extracted from donated tissue samples (see 18.2). Blood will be collected at the treating hospital. Patients will also be asked to complete a family history questionnaire.

#### 18.2 Molecular Correlates of Fractionation Sensitivity and Local Tumour Relapse

Local tumour relapse remains a clinical problem in a minority of women. The likelihood of local relapse may be influenced by genetically regulated factors, including the extent of intraductal spread and radiation resistance. Genome-wide approaches offer scope to

identify DNA sequence differences (mutations and polymorphisms) between tumours that discriminate between patients who suffer a local relapse and those who remain disease-free. Relapses that occur close to the site of the primary tumour are assumed to be true local recurrences (sharing the same gene mutations), whereas those occurring elsewhere in the breast and often at a later point in time are assumed to be new primaries (with differences in mutations compared to the primary tumour). Genomics offer scope for investigating the genetic relationships between ipsilateral and contralateral tumour relapse and primary tumour in a systematic way that may guide future local therapies. It is also possible to investigate loss of heterozygosity (LOH) in breast cancer by comparing DNA extracted from the tumour samples with DNA extracted from the blood samples (see 18.1). For LOH studies, a sample of the donated blood stored at the Institute of Cancer Research, Sutton, Surrey will be requested. It is proposed to establish tissue arrays and to extract DNA and RNA from paraffin blocks of primary tumours and ipsilateral and contralateral relapses/new primaries. Paraffin blocks containing the primary tumour and any subsequent recurrence/new primary from either breast will be sent to KCL/Guy's and St. Thomas' Hospital Breast Tissue Bank, London, where they will be stored for future analysis. In some centres, samples described above will be fresh frozen and sent to KCL/Guy's and St. Thomas' Hospital Breast Tissue Bank for the same analyses. The KCL/Guy's and St. Thomas' Breast Tissue Bank is a Human Tissue Authority licensed facility. After tissue cores and sections have been taken, the tumour paraffin blocks will be returned to the relevant pathology laboratory.

It is likely that breast cancers are heterogeneous in their sensitivity to fraction size. If so, it may be possible to distinguish subgroups of patients suited to treatment with large or small fractions based on examination of the tumour phenotype. Immunohistochemistry provides measures of tumour proliferation, hypoxia and DNA damage response status and other factors postulated to influence fractionation sensitivity. It is proposed to create tissue arrays from the primary tumour for future analysis of factors predicting sensitivity to radiotherapy fraction size.

#### 18.3 Quality of Life Study

The quality of life study will be implemented once the acute toxicity study has finished i.e. after the first 150 patients have been recruited into the trial.

There is evidence that radiotherapy causes long-term effects on quality of life in terms of altered breast appearance, breast, arm and shoulder symptoms, as well as a possible impact on some general aspects of QL such as fatigue. Results from the START trial have highlighted the value of patients' self-reported post-radiotherapy symptoms in discriminating between RT regimens in favour of hypofractionation [22]. Experience of the START trials showed that patient-rated cancer specific QL data, obtained with the EORTC QLQ-C30 [16] provided useful data at baseline (for example concerning the effects of surgery) [23] and also made a small contribution to a comparison of the regimens up to 2 years, fewer changes in parameters were observed from 2-5 years (unpublished data 2010). The FAST-Forward QL sub study is planned to provide subjective views of key breast symptoms and, body image over 10 years of follow-up and thus to add supportive data in the comparison of a trade off between local tumour control and adverse effects of treatment. The key effects of radiotherapy on QL are hypothesised to be on a range of breast symptoms as reported for the START trial [22] and potentially on body image plus short term general effects such as fatigue. Patient-reported arm and shoulder symptoms associated with RT are expected to be minimal since lymphatic RT is not allowed in the FAST-Forward trial. In the START trials these symptoms largely related to prior surgery [22].

The QL study is detailed in Appendix 4.

#### 19. TRIAL MANAGEMENT

#### 19.1 Trial Management Group

A Trial Management Group (TMG) will be set up and will include the Chief Investigator, Chief Clinical Co-ordinators, ICR-CTSU Scientific Lead and identified collaborators, the Trial Statistician and the Trial Managers. Principal Investigators and key study personnel will be invited to join the TMG as appropriate to ensure representation from a range of centres and professional groups. Notwithstanding the legal obligations of the Sponsor and Chief Investigator, the TMG have operational responsibility for the conduct of the trial. Where possible membership will include at least one lay/consumer representative. The Committee's terms of reference, roles and responsibilities will be defined in a charter issued by ICR-CTSU and based on MRC Good Clinical Practice (MRC GCP).

#### 19.2 Trial Steering Committee

A Trial Steering Committee (TSC) will be set up and will include an independent Chairman (not involved directly in the trial other than as a member of the TSC), not less than two other independent members, the Chief Investigator and one or two Principal Investigators. It is the role of the TSC to monitor progress of the trial and to ensure there is adherence to the protocol and the principles of Good Clinical Practice. The Committee's terms of reference, roles and responsibilities will be defined in a charter issued by ICR-CTSU and based on MRC GCP.

